### 3.1.1 Stratification, Randomization, and Blinding

Subjects will be randomized in a 1:1 ratio to either continue or withdraw from MMF. Given the relatively small number of subjects expected per site and the importance of ensuring balance on key disease-defining characteristics an adaptive procedure based on Frane [31] minimization concepts will be used to increase the likelihood of balance in treatment arms. The baseline characteristics that will be considered are study site, disease manifestation (renal disease, which will include subjects who presently have renal disease as well as those who have had renal manifestations in the past, versus non-renal disease, which will include subjects who have never had renal disease), and baseline MMF dose (< 2000 mg per day versus  $\geq 2000$  mg per day).

Subjects and investigational staff responsible for clinical care will not be blinded to the randomized treatment assignment. The cumbersome scheme that would have been needed to maintain the blind required that subjects take different numbers of pills from multiple bottles. Implementation of the scheme would have placed undue burden on the subjects and had a high potential for dosing errors. Knowledge of the assigned treatment also has the advantage of facilitating rapid response in the event of a serious flare.

Unblinding the trial has the potential to impact the estimated rates of disease reactivation, because the definition of this endpoint includes subjective elements. In order to assess the magnitude and direction of the impact on these estimates, a second blinded clinician will also conduct the physical exams scheduled for Weeks 8, 12, 16, and 20. If at Week 20, the subject has a mild/moderate or severe SELENA-SLEDAI flare, the blinded physician should also participate in the Week 24 visit. These time points were selected, because we anticipate that most flares will occur early in the study. The blinded physician will also receive any additional blinded subject records needed to complete the SELENA-SLEDAI and a questionnaire about the need to change medications. This information will be used to compare the rate of disease reactivation among blinded and unblinded assessors.

Statistical and project staff at the SACCC and the DAIT Medical Monitor and Project Manager will be unblinded to individual treatment assignments as well.

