#### 7.1.2. Assessment Time Windows

Allowable visit windows for all scheduled visits are provided in Table 7-1.

 Visit
 Window

 Screening
 -28 to -1

 Baseline
 0

 Weeks 4, 8, 12, 16, 20, 24, 32, 40, 48, 60
 ± 7 days

Table 7-1 Visit Windows

Unscheduled, Flare, and Endpoint visits may also occur throughout the study. All data will be included in analyses, regardless of time of assessment.

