# 7.2. Primary Endpoint

# 7.2.1. Computation of the Primary Endpoint

The primary endpoint is the probability in each arm of experiencing clinically significant disease reactivation by 60 weeks after randomization. The 60-week time point is to allow 48 weeks of observation off MMF in the withdrawal arm and minimize dropout, which is likely to occur as the trial lengthens. Clinically significant SLE reactivation requires both:

- 1) A SELENA-SLEDAI\*-defined mild/moderate or severe flare, and
- 2) Increased immunosuppressive therapy on a sustained basis as defined by one of the following criteria:
  - a. Sustained activity: Subject has significant prolonged SLE flare requiring steroid increase/burst to ≥ 15 mg/day prednisone (or its equivalent) for more than four weeks.
  - b. Frequent relapsing/remitting:
    - Subject flares requiring an increase/burst of steroids and is successfully tapered to < 15 mg/day within four weeks, but this occurs on two or more occasions. or
    - ii. Intra-articular, intra-muscular or IV steroids, on more than one occasion.
  - c. Clinical activity of sufficient severity to warrant resumption of or an increased dose of MMF or addition of other major immunosuppressive including azathioprine or methotrexate. Regardless of steroid use, if the investigator observes disease activity of sufficient severity to warrant resumption, addition or increase in dosage of major immunosuppressant in the setting of a SELENA-SLEDAI\*-defined flare, subject has met the primary endpoint.

Version: 1.0 Page 16 of 48

\*ALE06 will typically use a spot urine protein:creatinine ratio rather than a 24-hour urine assessment for the SELENA-SLEDAI. However, if indicated, results from a 24-hour urine collection may be used.

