# **Endpoint:**

For each subject, a yes/no variable will be assigned to indicate whether a subject has met the primary endpoint of clinically significant disease reactivation between Day 0 and Week 60, as defined above.

Subjects who terminate early from the study, and who had not previously met primary endpoint, will be handled as follows:

- 1. Subjects who do not have a mild/moderate or severe SELENA-SLEDAI flare at their last study visit will be categorized as not experiencing clinically significant disease reactivation.
- 2. Subjects who have a mild/moderate or severe SELENA-SLEDAI flare at their last study visit:
  - a. Subjects will be categorized as experiencing clinically significant disease reactivation for the following three scenarios:
    - i. Subject has a SELENA-SLEDAI mild/moderate or severe flare at the time of early termination, and a steroid increase/burst to ≥ 15 mg/day prednisone that is sustained through end of study.
    - Subject previously experienced a flare requiring either intraarticular, intra-muscular or IV steroids, or an increase/burst of steroids that was successfully tapered to < 15 mg/day within four

Version: 1.0 Page 18 of 48

<sup>1 For ALE06, prednisone > 0.5 mg/kg/day is categorized as a severe SELENA-SLEDAI flare if the duration is >2 weeks. Increases in prednisone >0.5 mg/kg/day but for ≤2 weeks will be categorized as mild/moderate SELENA-SLEDAI flares.

weeks, and is experiencing a severe flare at the time of early termination.

- iii. Subject has a SELENA-SLEDAI severe flare based on the following clinical components: SLEDAI score; New/Worse disease, and Increase in PhGA without considering prednisone or other treatments
- b. Subjects experiencing flare at the time of early termination, but who do not met the criteria in 2.a. above, will be classified as not experiencing clinically significant disease reactivation.

These cases will be re-categorized under sensitivity analyses for the primary endpoint (see 7.2.3).

The time of clinically significant disease reactivation is defined as the date of the first SELENA-SLEDAI assessment that meets (or goes on to meet) the criteria for clinically significant SLE reactivation. The time-to-event will be defined as the interval: date of disease reactivation – date of Day 0 visit. Subjects who do not experience clinically significant disease will be censored at the last visit date on study.

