The probability, or risk, of disease reactivation by Week 60 (on a 0 to 1 scale) in each arm will be derived using the Kaplan-Meier product-limit estimator for the cumulative incidence of disease reactivation. Standard errors and confidence intervals for the cumulative incidence will be obtained using Greenwood's formula.

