# 7.3.2. Probability of Experiencing a SELENA-SLEDAI Flare

**Endpoint**: The SELENA-SLEDAI instrument will be completed at baseline and every follow-up visit, including any Flare or Endpoint visits, during the course of the 60 week study period for all subjects. The SELENA-SLEDAI assesses SLE disease activity and flares based on changes in the SLEDAI score, the Physician's Global Assessment (PGA), medication use (prednisone, NSAIDS, Plaquenil, major immunosuppressives), other disease activity criteria, and hospitalization due to SLE. See Section 7.2.1., *Computation of the Primary Endpoint*, for more information on scoring of the SELENA-SLEDAI flare assessment.

For each subject, a yes/no variable will be created to indicate whether a subject had at least one mild/moderate or severe SELENA-SLEDAI flare by Week 60 and separately whether the subject had at least one severe SELENA-SLEDAI flare by Week 60. Subjects who terminate early from the study prior to experiencing any SELENA-SLEDAI flare will be categorized as not experiencing any SELENA-SLEDAI flare by Week 60.

Additionally, for each subject, the total number of visits with mild/moderate or severe SELENA-SLEDAI flares will be tabulated, including categorizing number of flare visits for a subject into 0, 1, or >1 flare.

The probability of experiencing any SELENA-SLEDAI flare and the probability of experiencing any severe SELENA-SLEDAI flare by Week 60 will be calculated in aggregate and within subgroups defined by disease manifestation (renal disease/extra-renal disease) and by baseline MMF dosing group (<2000 mg per day / ≥ 2000 mg per day).

**Analysis**: Analyses analogous to those specified for the primary endpoint (effect estimates and 95% confidence intervals, risk difference, and summaries of increased risk ( $\alpha$ ) vs.% confidence the "true" risk is  $\leq \alpha$ ) will be performed for the probability of experiencing any SELENA-SLEDAl flare and any severe SELENA-SLEDAl flare by Week 60, including analyses within subgroups for disease manifestation and baseline MMF dose. See Section 7.2.2, *Primary Analysis of the Primary Endpoint*, for more details on the analyses.

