#### 7.3.3. Time to First SELENA-SLEDAI Flare

**Endpoint**: The SELENA-SLEDAI instrument will be completed at baseline and every follow-up visit during the course of the 60 week study period for all subjects. The SELENA-SLEDAI assesses flares based on changes in the SLEDAI score, the Physician's Global Assessment (PGA), medication use (prednisone, NSAIDS, Plaquenil, major immunosuppressives), other disease activity criteria, and hospitalization due to SLE. See Section 7.2.1., *Computation of the Primary Endpoint*, for more information on scoring of the SELENA-SLEDAI flare assessment.

For each subject, time from Day 0 to first SELENA-SLEDAI flare and time to first severe SELENA-SLEDAI flare will be calculated in study days as: date of first flare – date of Day 0 visit. Subjects who do not experience SELENA-SLEDAI flare will be censored at their last visit date on study.

**Analysis**: Analyses analogous to those specified in Section 7.3.1, *Time to Clinically Significant Disease Reactivation*, will be performed for time to SELENA-SLEDAI flare. Additionally, sensitivity analysis may be run to assess the impact of new or increased major immunosuppressives as the only cause of severe flare. Subjects who re-start or increase major immunosuppressives, but have no other disease activity that would categorize them as having a severe flare, will be categorized as not having a severe SELENA-SLEDAI flare (i.e. categorized as a mild/moderate flare) and analyses would be replicated using this definition of a severe flare.

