#### 12. CHANGES TO THE ANALYSES PLANNED IN THE PROTOCOL

[figure not shown]
- Section 7.2. Primary Endpoint. Statistical methods to obtain effect estimates and confidence intervals for the probability of observing clinically significant disease reactivation by 60 weeks have been changed from exact methods for complete data (proportions with Clopper Pearson intervals) to Kaplan-Meier predict-limit estimators to allow for censoring of subjects who terminated early without evidence of disease reactivation.
- 2. Section 7.3.3. Time to First SELENA-SLEDAI Flare: Time to first SELENA-SLEDAI flare has been changed from using withdrawal date to using Day 0 date. This allows us to calculate time to first SELENA-SLEDAI flare in both arms, since the Maintenance arm does not start withdrawal, and is consistent with the timing of the time to disease reactivation endpoint specified in Section 7.3.1.
- 3. Section 7.3.6. Probability of Experiencing a BILAG A or B Flare: This is a new endpoint was added to the SAP by the study team.
- 4. Section 11.1. Interim Analysis: The sample size re-estimation specified if ≤ 10% of the first 80 subjects experienced disease reactivation was not performed. We observed that after 60 weeks of post-randomization, 8 of the first 80 (10%) subjects experienced disease reactivation. Although the rate of disease reactivation was low, the team opted not to re-estimate the sample size. Rates of BILAG and SELENA-SLEDAI flares, which will also be important for evaluating the impact of MMF withdrawal, are higher than 10%. The larger sample size is necessary to improve precision for these important secondary endpoints and will strengthen the primary analysis.

Version: 1.0 Page 36 of 48

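### Minor: the Kaplan-Meier risk by Week 60 runs on actual visit dates with no common Week-60 analysis time, so an event first found at that visit is weighted by its scheduling day

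*SAP*

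**What the plan says.** The endpoint in SAP 7.2.1 is the probability of "experiencing clinically significant disease reactivation by 60 weeks after randomization". Each subject gets a yes/no variable for Day 0 to Week 60, but the reported estimate does not come from it. The risk "of disease reactivation by Week 60 (on a 0 to 1 scale) in each arm will be derived using the Kaplan-Meier product-limit estimator", with Greenwood standard errors, and SAP 7.2.2 builds the risk difference and the confidence curve on that estimate.

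Event time is the date of the qualifying SELENA-SLEDAI assessment minus the Day 0 date. For everyone else, "Subjects who do not experience clinically significant disease will be censored at the last visit date on study".

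SAP 7.1.2 allows the Week-60 visit 7 days either side and adds: "All data will be included in analyses, regardless of time of assessment". SAP 7.3.1 lists Week 60 among the reporting times of the curve without giving it a study day.

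SAP Section 12 explains the move from simple proportions to Kaplan-Meier as made "to allow for censoring of subjects who terminated early without evidence of disease reactivation". For time to first flare, SAP 7.3.3 repeats the censoring rule: "Subjects who do not experience SELENA-SLEDAI flare will be censored at their last visit date on study".

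**The concern.** The switch to Kaplan-Meier was meant for subjects who leave early. On actual dates it also censors completers, one after another, through a 15-day window around Day 420 (60 x 7). An event first found at the Week-60 visit therefore counts for more or less according to the appointment day, and the direction depends on where the curve is read.

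- Read at Day 420: an event on Days 421-427 is left out, although the yes/no variable counts that subject. An event late in Days 413-420 is somewhat over-weighted.
- Read at Day 427 or at the end of the curve: every event is kept, but a late one is divided by the few subjects not yet censored.

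SAP 7.2.2 invites physicians and patients to read a decision from a single curve. SAP Section 12 reports only 8 reactivations among the first 80 subjects, so one event placed by a scheduling day can be visible in that curve.

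**Working it through.** **The plan's own figure.** Protocol Table 8.1 gives 85% power for maintenance risk 0.05, increase 0.05, *a* = 0.15, 60 per arm and one-sided 85% confidence. With simple proportions, SE = sqrt[(0.05 x 0.95 + 0.10 x 0.90)/60] = 0.0479, and power = Phi(0.10/0.0479 - 1.036) = Phi(1.05) = 85.4%. All filled cells of the table agree within 2 points. The table is reproduced by simple proportions, so this point does not touch it.

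**Example (assumed).** There are 60 per arm and no early leavers. Maintenance has 3 events, none at Week 60. Withdrawal has 5 earlier events and one first dated at the Week-60 visit. The 54 withdrawal-arm completers are spread evenly over Days 413-427 (54/15 = 3.6 per day).

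Formulas, with n at risk when the late event occurs:
- Risk = 1 - (55/60)(1 - 1/n)
- Greenwood variance = S² x [5/(60 x 55) + 1/(n(n - 1))], where S = 1 - risk
- Maintenance variance = 0.05 x 0.95/60 = 0.00079
- Confidence = Phi((*a* - RD)/SE), where SE is the root of the summed variances

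| Late event | n | Risk | RD | SE | Confidence at *a* = 0.15 |
|---|---|---|---|---|---|
| Common nominal time | 55 | 0.100 | 0.050 | 0.048 | 98% |
| Day 420 (either reading) | 29 | 0.115 | 0.065 | 0.054 | 94% |
| Days 421-427, read at Day 420 | dropped | 0.083 | 0.033 | 0.045 | 99.5% |
| Day 424, read at Day 427 or end | 15 | 0.144 | 0.094 | 0.073 | 78% |
| Day 427, read at Day 427 or end | 4 | 0.31 | 0.26 | 0.20 | 29% |

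Day 424 in full: 1 - 0.9167 x 14/15 = 0.144; variance 0.8556² x (0.001515 + 0.004762) = 0.00459; SE = sqrt(0.00459 + 0.00079) = 0.073; (0.15 - 0.094)/0.073 = 0.76; Phi = 78%.

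The last row depends heavily on how completers are allotted to days. With 2 at risk instead of 4, the risk is 1 - 0.9167/2 = 0.54. With one at risk it is 1.00.

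**Average effect.** Simulation used 60 per arm, risks 0.10 v 0.05, 10% dropout, and Week-60 visits uniform over Days 413-427. The share of events first dated at Week 60 is an assumption.

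- Read at Day 420, shares from 2% to 20%: the mean risk difference falls by 0.0003 to 0.003, against an SD of 0.049.
- Read at the end of the curve: the mean rises by about 0.002 at a 2% share and 0.005 at 5%. The SD rises from 0.049 to about 0.06-0.07 at 2% and about 0.08 at 5%. It varies between runs because a few extreme arms drive it.

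**The case against.** The strongest reply is that few primary events can first be dated at Week 60, and much of this stands. Criterion 2a needs more than four weeks of steroid and 2b needs repeated occasions. Events are dated back to the first assessment that goes on to qualify, so a Week-60 event would qualify mostly through 2c. Protocol 3.1 brings flaring subjects in between visits, and Protocol 3.1.1 chose its blinded assessments "because we anticipate that most flares will occur early in the study". A constant-hazard simulation without flare visits gives about 1.1 Week-60 events per arm at risk 0.10; that is best treated as an upper bound.

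It is also said that actual dates are conventional in Kaplan-Meier work, that the reading day belongs in programming specifications, and that the analysis is descriptive. That supports a low grade. It does not remove the point, because the SAP's stated censoring rule makes the result depend on appointment days under either reading.

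Three stronger readings are tempting, and the documents do not support them.

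- A reader might infer that the SAP discards events after Day 420. No section sets that cut-off, and the inclusion sentence in SAP 7.1.2 points the other way.
- A reader might infer that the primary result or the sample size is materially undermined. The mean shifts are small and Table 8.1 is unaffected.
- A reader might infer that the flare risks in SAP 7.3.2 certainly share the defect. That section calls for "Analyses analogous to those specified for the primary endpoint (effect estimates and 95% confidence intervals, risk difference" and refers to SAP 7.2.2. But it classes subjects who leave before any flare as having none, and SAP Section 12 records the change of method only for the primary endpoint. Kaplan-Meier there is an inference.

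**Conclusion.** The point holds as a minor one. The SAP times events and completer censoring by actual dates across Days 413-427 and names no common Week-60 time. The primary risk can therefore change with a scheduling day while patients and disease stay the same.

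The size depends on the reading day. At Day 420 the average effect is negligible. At Day 427 or the curve's end, which fits SAP 7.1.2 better, a single late-window event can move the risk substantially: 0.100 to 0.144 on Day 424 and to about 0.31 on Day 427, in the example. The direction follows from the rule. The figures rest on the assumed event counts, even spread of visits and absence of early leavers, and the simulations on the assumed share of events first dated at Week 60.

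**What to change.** In SAP 7.2.1 and 7.2.2, give every subject's scheduled Week-60 visit one nominal time, Day 420. Apply this to events and completer censorings alike, including a visit held outside its window. Order events before censorings at ties and read the risk at Day 420. With no early leavers the estimate then equals the simple proportion: 6/60 = 0.100 in the example, whatever the visit day.

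Early-withdrawal visits and interim Flare or Endpoint visits keep their actual dates. No separate exclusion of events dated after the window should be added; it would conflict with SAP 7.1.2 and only move the cut-off.

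Use the same rule for time to first flare (SAP 7.3.3), and for the flare risks in SAP 7.3.2 if they too are estimated by Kaplan-Meier; the SAP should say whether they are.

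The cost is one or two sentences and one derived time variable. No new data are needed and the clinical definition of reactivation is unchanged. Settling it before analysis also removes a choice of reading day once results are known.

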# 7.2.2. Primary Analysis of the Primary Endpoint

The planned analyses for this study are designed to maximize the information available for medical decision-making. The planned analyses are as follows:

Effect estimates and 95% confidence intervals for the risk of disease reactivation by Week 60 in each arm as well as the estimated risk difference (i.e. risk\_MMFwithdrawal - risk\_MMF maintenance) and 95% confidence intervals around the risk difference will be reported using the Kaplan-Meier product-limit estimator.

The observed risk estimates will be used to compute the "% Confidence that the true increase is  $\leq$  a" as a function of values for the "Acceptable increase in risk with withdrawal of MMF (a)". This information will be plotted with values for "Acceptable increase in risk with withdrawal of MMF (a)" on the x axis and estimates for "% Confidence that the true increase is  $\leq$  a" on the y axis. The study will generate a single curve based on the observed risk estimates for the two arms. Physicians with their patients could decide on an acceptable level of increased risk (a) then read from the plot the % confidence that this selected value of a would not be exceeded with withdrawal of MMF. Depending on the level of confidence, they may or may not decide to withdraw MMF.

Version: 1.0 Page 19 of 48

The motivation for the curve comes from the test of non-inferiority with the following hypotheses:

 $H_0$ : the increase in risk with withdrawal of MMF ( $\mathbf{T}$ )  $\geq \mathbf{a}$ , and  $H_A$ : the increase in risk with withdrawal of MMF ( $\mathbf{T}$ )  $< \mathbf{a}$ , where  $\mathbf{a}$  is some value for the acceptable increase in risk.

The  $H_0$  hypothesis would be rejected in favor of  $H_A$  if the upper (1- $\alpha$ ) % confident limit about the estimated risk difference (i.e. risk\_MMFwithdrawal - risk\_MMF maintenance) is less than  $\boldsymbol{a}$ . Then, we could conclude that  $\boldsymbol{T} < \boldsymbol{a}$  with (1- $\alpha$ )% confidence. Physicians and patients who are comfortable with both a risk increase of no more than  $\boldsymbol{a}$  and a confidence level of (1- $\alpha$ )% could conclude that withdrawal from MMF is "not unacceptably worse" than maintenance on MMF.

Recognizing that the appropriate value of  ${\it a}$  will be highly variable among physicians and patients, a single hypothesis is not defined for this study. Alternatively the upper 1-sided (1- $\alpha$ )% confidence limit (UCL) for the observed risk difference will be computed for values of  $\alpha$  ranging from 0 to 0.99, in 0.01 increments. Note that for a given value of  $\alpha$  the computed UCL equals the value of  ${\it a}$ , at which a null hypothesis could be rejected with a Type I error rate of  $\alpha$ . Results of these computations will be tabulated and plotted.

The primary analyses of the primary endpoint will be performed on the mITT population.

